8.3. Lost to Follow Up

A participant will be considered lost to follow-up if he or she repeatedly fails to return for scheduled visits and is unable to be contacted by the study site.

The following actions must be taken if a participant fails to return to the clinic for a required study visit:

- The site must attempt to contact the participant and reschedule the missed visit as soon as possible and counsel the participant on the importance of maintaining the assigned visit schedule and ascertain whether or not the participant wishes to and/or should continue in the study.
- Before a participant is deemed lost to follow up, the investigator or designee must make every effort to regain contact with the participant (where possible, 3 telephone calls and, if necessary, a certified letter to the participant's last known mailing address or local equivalent methods). These contact attempts should be documented in the participant's medical record.
- Should the participant continue to be unreachable, he/she will be considered to have withdrawn from the study with a primary reason of lost to follow-up.

9. STUDY ASSESSMENTS AND PROCEDURES

- Study procedures and their timing are summarized in the SoA.
- Protocol waivers or exemptions are not allowed.
- Immediate safety concerns should be discussed with the sponsor immediately upon occurrence or awareness to determine if the participant should continue or discontinue study treatment.
- Adherence to the study design requirements, including those specified in the SoA, is essential and required for study conduct.
- All screening evaluations must be completed and reviewed to confirm that potential participants meet all eligibility criteria. The investigator will maintain a screening log to record details of all participants screened and to confirm eligibility or record reasons for screening failure, as applicable.
- Procedures conducted as part of the participant's routine clinical management (e.g., blood count) and obtained before signing of ICF may be utilized for screening or baseline purposes providing the procedure met the protocol-specified criteria and was performed within the time frame defined in the SoA.

9.1. Efficacy Assessments

9.1.1. HES Flare

A HES flare is defined as an HES-related clinical manifestation based on a physician-documented change in clinical signs or symptoms (worsening symptoms and/or elevated blood eosinophil level) resulting in the need for either of the following:

- An increase from the most recent dose in the maintenance OCS dose (prednisone/prednisolone equivalent) by at least 10mg/day for 5 days
- An increase in or addition of any cytotoxic and/or immunosuppressive HES therapy from/to the most recent dose of HES therapy.

To be considered as an HES flare, the most recent dose of HES therapy must not have changed for at least 4 weeks. This ensures that failed reductions in HES therapy are not misclassified as an HES flare.

The start date for an HES flare will be defined as the date of therapy escalation confirmed by the investigator attributable to an HES-related clinical manifestation.

When a subject experiences an HES flare, the investigator will monitor the change in disease control per routine medical care (e.g., follow-up call) and record the resolution of the flare including the end date. Investigators are encouraged, as medically appropriate, to return the subject's treatment regimen to the level prior to the flare after the flare has resolved.

In the event of disease worsening for which the investigator suspects an HES flare between scheduled clinic visits, when possible, the subject will return to the clinic to have the unscheduled 'Flare' visit assessment completed as described in the SoA. When attending the clinic visit at the time of a suspected HES flare is not possible, the investigator should make every effort to evaluate the subject via telephone and complete the HES Core Assessments (Section 9.1.2). If an escalation of therapy is initiated by a non-study physician, the investigator should confirm that the escalation in therapy is attributable to an HES-related clinical manifestation.

Investigators will be required to record details pertaining to the HES flare event in the CRF from Visit 1 until 20 weeks after the first dose of mepolizumab. This should include details regarding the clinical symptoms resulting in the flare with detail of the required intervention(s), e.g., OCS dose increase, *or* addition or escalation of immunosuppressive or cytotoxic therapy. In addition, all other relevant clinical, laboratory or other diagnostic investigations required to confirm the flare must be captured in the CRF.

The definition of HES flare for this study (205203) is different from that for the preceding, randomized Study 200622. This difference in definitions is due to the requirement during Study 200622 to avoid decreases in background HES therapy that may confound a blinded subject's clinical status. In Study 205203, all participants will receive mepolizumab and investigators will be unblinded to blood eosinophil levels starting 4 weeks after the first dose (Visit 2) so that they may adjust background HES therapy as per SoC.

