9.1.2. HES Core Assessments (Clinician Assessment)

Clinical evaluation by the investigator will be guided by the HES Core Assessments, consisting of clinical signs and symptoms that reflect the heterogeneous nature of HES observed in clinical practice. During the study, the investigator will evaluate participants

at each clinic visit using the HES Core Assessments and determine whether worsening of signs/symptoms supports an increase in HES therapy. In addition, to further characterize the basis for determination of flare and increase in therapy, the investigator will prepare a narrative for each HES flare.

The HES Core Assessments will characterize each subject's clinical manifestations at baseline and monitor for changes throughout the study. The investigator will be asked to rule out other possible etiologies for the change in clinical symptoms, such as an infection, prior to diagnosing an HES flare. For the "others" category in [Table 1](#), specific components of the physical exam will be used as part of the baseline core assessments and throughout the study to monitor for the presence or absence of changes in exam findings. Findings of the HES Core assessments will be recorded in the electronic device.

Table 1 HES Core Assessments

Symptoms	Assessment
Constitutional	
Fatigue Pain (including but not limited to muscle, joint, general pain) Angioedema (swelling under the skin)	Each symptom rated using a 0-3 scale
Dermatologic	
Rash Itch Hives Others (specify)	Each symptom rated using a 0-3 scale
Gastrointestinal	
Average number of vomiting a day in the past week Average number of diarrhea a day in the past week Average number of stools a day in the past week Abdominal pain Difficulty in swallowing food	Each symptom rated using a 0-3 scale
Respiratory	
Breathing symptoms such as shortness of breath and wheezing	0-3 scale
Dyspnea (shortness of breath)	0-3 scale
Cough	0-3 scale

Symptoms	Assessment
Sinus-related symptoms: Nasal congestion Sinus headache/facial pain/pressure Postnasal drip (drainage down the back of the throat) Purulent rhinorrhea (discoloured & thick nasal discharge) Ear fullness	Each symptom rated using a 0-3 scale
Cardiovascular	
Heart failure classification for functional capacity	Classes I-IV
Heart failure classification for objective assessment	Classes: A-D
Neurologic	
Sensory Motor Cognitive and Mental status change	Each symptom rated using a 0-3 scale
Others	

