9. EFFICACY ANALYSES

9.1. Exploratory Efficacy Analyses

9.1.1. Rate of HES Flares

9.1.1.1. Endpoint / Variables

Definition of HES Flare

A HES flare is defined as an HES-related clinical manifestation based on a physician-documented change in clinical signs or symptoms (worsening symptoms and/or elevated blood eosinophil level) resulting in the need for either of the following:

- An increase from the most recent dose in the maintenance OCS dose (prednisone/prednisolone equivalent) by at least 10mg/day for 5 days
- An increase in or addition of any cytotoxic and/or immunosuppressive HES therapy from/to the most recent dose of HES therapy.

To be considered as an HES flare, the most recent dose of HES therapy must not have changed for at least 4 weeks. This ensures that failed reductions in HES therapy are not misclassified as an HES flare.

The definition of HES flare for this study (205203) is different from that for the preceding, randomized Study 200622. This difference in definitions is due to the requirement during Study 200622 to avoid decreases in background HES therapy that may confound a blinded subject's clinical status as well as the requirement during Study 200622 to blind blood eosinophil levels. In Study 205203, all participants will receive mepolizumab and investigators will be unblinded to blood eosinophil levels starting 4 weeks after the first dose (Visit 2) so that they may adjust background HES therapy as per standard of care (SoC).

Derivation of Endpoint

The rate of HES flares will be calculated for each subject as the number of observed HES flares divided by the time (expressed in years) between the first dose of study treatment in Study 205203 and either the Week 20 visit date if available, or otherwise the study withdrawal date (see Section [13.4.4](#)).

The rate of HES flares will also be calculated separately using data from Study 200622 only, for those subjects continuing into Study 205203.

The number of observed HES flares will be calculated for each subject as the number of unique starting dates for HES flares. To be considered as a separate episode of HES flare, the onset date of an HES flare must be at least 14 days apart from the resolution date of the preceding HES flare.

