9.1.1.4. Statistical Analyses / Methods

Endpoint
Rate of HES flares.
Model Specification

 Analysis using a negative binomial generalised linear model with a log-link function, including terms for baseline OCS dose from study 200622 (continuous scale), region and observed time (as an offset variable). The model estimated mean flare rate per year will be weighted according to the observed proportion of the categorical covariates in the study data by inclusion of the OM (obsmargins) option in the LSMEANS statement of the GENMOD procedure. A separate model will be fitted to data from Study 200622 for those subjects continuing into Study 205203.
Model Checking & Diagnostics

 The fit of the negative binomial generalised linear model will be investigated by calculating and plotting standardised deviance residuals.
Model Results Presentation

 Median rate/year on raw data values for Study 200622 (Week 0 – Week 32, double-blind) and Study 205203 (Week 32 – Week 52, open-label). Adjusted mean rate/year from negative binomial model and 95% confidence interval for Study 200622 (Week 0 – Week 32, double-blind) and Study 205203 (Week 32 – Week 52, open-label).
Subgroup Analyses

 No subgroup analyses will be performed on this endpoint.
Sensitivity and Supportive Statistical Analyses

 No sensitivity analyses will be performed

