13.2. Appendix 2: Study Phases and Treatment Emergent Adverse Events

Assessments and events will be classified according to the time of occurrence relative to the first dose of open-label mepolizumab.

Time	Subjects completing the study (Week 20 visit)	Subjects not completing the study (Predicted Week 20 visit date = Date of first dose + 140 days)
Total observed time	Week 20 visit date – date of first dose + 1 day	Study withdrawal date – date of first dose + 1 day
Time on treatment (days)	Minimum(Week 20 visit date, Date of last dose + 28 days) - Date of first dose + 1 day	Minimum(Study withdrawal date, Date of last dose + 28 days) - Date of first dose + 1 day
Time off treatment (days)	Week 20 visit date – Minimum(Week 20 visit date, Date of last dose + 28 days)	Study withdrawal date – Minimum(Study withdrawal date, Date of last dose + 28 days)
Missing time	0	Predicted Week 20 visit date – Study withdrawal date

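### Does the 4-week unchanged-therapy rule distort the 205203 flare rate, given that all follow-up time stays in the denominator?

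*Protocol*

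**What the plan says.** Protocol 9.1.1, repeated in SAP 9.1.1.1 and 13.4.4, makes an escalation of HES therapy a flare only under a stability condition: "To be considered as an HES flare, the most recent dose of HES therapy must not have changed for at least 4 weeks". The reason given is that an unsuccessful taper should not be recorded as a flare.

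The rate in SAP 9.1.1.1 is the flare count "divided by the time (expressed in years) between the first dose of study treatment in Study 205203 and either the Week 20 visit date", or the study withdrawal date if there is no Week 20 visit. The negative binomial model in SAP 9.1.1.4 includes "region and observed time (as an offset variable"). No days are removed for periods in which an escalation could not count. The same section states "No sensitivity analyses will be performed".

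Three other provisions bear on the point:

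- Investigators may adjust background therapy from Visit 2 (Protocol 5.1), and Protocol 3.3.2 expects such adjustments.
- After a flare, Protocol 9.1.1 encourages return of the "treatment regimen to the level prior to the flare after the flare has resolved".
- For a second episode, SAP 9.1.1.1 requires that "the onset date of an HES flare must be at least 14 days apart from the resolution date of the preceding HES flare".

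Table 3.3 reports the 205203 rate together with a 200622 rate for the same participants. Each study has its own model.

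**The concern.** The numerator and denominator appear not to match. After a therapy change there are 28 days in which no escalation can become a flare, yet those days still count as time at risk. A low rate could mean few flares, or frequent changes that kept escalations from qualifying. Results are shown by previous treatment, so two groups that tapered to different extents could differ for that reason alone.

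The rule also looks incomplete. It does not say whether a change in any HES therapy restarts the 4 weeks or only a change in the drug being escalated, whether increases count as changes, or whether the return to the earlier regimen after a flare does so. Finally, Table 3.3 sets the rate beside one obtained under largely fixed therapy and a different flare definition, which invites a comparison that the two numbers may not support.

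**Working it through.** The plan states no expected flare rate or number of therapy changes, so there is no figure to reproduce. The arithmetic shows the possible scale only.

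**1. Denominator.** SAP 13.2 gives "Predicted Week 20 visit date = Date of first dose + 140 days". SAP 13.4.4 adds one day, so a completer at the nominal visit contributes 140 + 1 = 141 days.

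**2. One isolated change.** Blocked time is 28/141 = 19.9%, leaving 113 days. This equals the share of escalations left out only if risk is constant. With risk multiplied by m in the 28 days after the change, the share is 28m/(113 + 28m):

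- m = 2: 56/169 = 33.1%
- m = 3: 84/197 = 42.6%

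So 19.9% is not an upper bound.

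**3. Several changes.** Two or three changes at successive 4-weekly visits block 56 or 84 days (39.7% or 59.6%). If spaced 14 days apart they overlap and block 42 or 56 days (29.8% or 39.7%).

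**4. Whole study.** Let a share s of participants have one change (assumed). The proportion left out is 28ms/(141 + 28(m − 1)s).

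| s | m = 1 | m = 2 | m = 3 |
|---|---|---|---|
| 20% | 4.0% | 7.6% | 11.0% |
| 50% | 9.9% | 18.1% | 24.9% |
| 80% | 15.9% | 27.4% | 36.2% |

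**5. Escalation decided at visits.** Protocol 9.1.2 has the investigator, at each clinic visit, "determine whether worsening of signs/symptoms supports an increase in HES therapy". If visits are exactly on schedule, the visit after a change is 28 days later and already qualifies, so nothing is lost. If each visit falls evenly on −7 to +7 days (assumed), the interval is under 28 days with probability 105/225 = 46.7%. The expected blocked interval is the sum over k = 1 to 14 of (15 − k)(28 − k)/225 = 2380/225 = 10.6 days. Over 140 days that is 7.6% per changed participant, at constant risk. If half of escalations start at once and half at visits, it is (19.9 + 7.6)/2 ≈ 13.7%.

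**6. Overlap with the 14-day rule.** Suppose a flare resolves, and the regimen is returned, 14 days after escalation, and the return restarts the clock (both assumed). An escalation 14 to 27 days after the return then passes the separation rule and fails the 4-week rule. To first order this affects 14 × (141 − 35)/141 = 10.5 days per escalation, or 1.4%, 2.9% and 5.8% at assumed rates of 0.5, 1 and 2 worsenings per year.

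**7. Would an eligible-time denominator be better?** Take a base rate of 1.0 per year, s = 50% and m = 2 (assumed). All escalations run at 155/141 = 1.10 per year and the planned rate is 127/141 = 0.90. Counted flares over eligible days give 1.00. That figure does not recover the all-escalation rate either. Its denominator is also defined after baseline, depends on the outcome, and rests on medication dates that SAP 13.5.2 may impute.

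**The case for a change.** The strongest case for a change is that the rule's wording (any change) is wider than its purpose (failed reductions), and that the output would not show the effect. SAP 9.1.1.3 names only discontinuation of study medication as an intercurrent event. The OCS displays, Tables 3.4 to 3.8, cannot show cytotoxic or immunosuppressive escalations. A supportive count of all escalations would use data already collected, and Table 3.3 labels its two periods as one 52-week timeline.

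The dependence on therapy changes is real, and the wording is indeed wider than its purpose. The rest weakens on inspection:

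- **Applying the rule.** The documents do not say who applies it, but they point to the investigator, who confirms the start date and writes a narrative for each flare (Protocol 9.1.1 and 9.1.2). Listing 11 is of investigator-reported flares. Nothing says that flares are re-adjudicated from medication dates, so the open questions need not be a programming gap.
- **The extra count.** It would put back the failed reductions that the protocol chose to exclude. For escalations never recorded as flares it would rest on the recorded reason for use, which need not show that a clinical worsening prompted the increase.
- **The two studies.** The difference in definition is stated in Protocol 9.1.1 and in SAP 9.1.1.1 and 13.4.4. No rate ratio is planned. The natural reading of SAP 9.1.1.1 is that the 200622 column uses that study's own definition.
- **Missing displays.** The shells for Tables 3.1 to 3.3 are not in the document (SAP 13.9), so neither a missing footnote nor a missing count can be established.

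One discrepancy stands apart from the rate. Protocol 9.1.1 describes return to the level before the flare, while SAP 13.4.4 describes return to the Visit 2 baseline. The two passages must be reconciled.

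**Conclusion.** No change to the planned analysis follows. The quantity reported is the number of flares, as the protocol defines them, per year of follow-up. Full observed time is the correct denominator for that quantity. It would mislead only if read as a rate of all escalations, as a rate per eligible day, or as directly comparable with 200622, and the plan claims none of these. The endpoint is exploratory, SAP 2.3 plans no hypothesis test, and the primary safety objective is unaffected.

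The share of escalations left out could range from none (visits on schedule, escalation only at visits) to 15.9% of the study total (80% of participants with one change each, constant risk). It would be higher with repeated changes or with raised risk after a change. These are scenarios; the documents do not supply the inputs.

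Which changes restart the 4 weeks, how that combines with the 14-day rule, and a note on comparability are details that the study team can settle in preparing the displays. A descriptive count of escalations failing the rule is optional. If produced, it would have to be labelled as including failed reductions and as limited by what the CRF captures.

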2. SCHEDULE OF ACTIVITIES (SOA)

Procedure	Screening/Baseline	20-Week Treatment Period					WD (4 weeks post-last dose) ± 1 wk	Study Visit 7 Additional follow-up (12 weeks post-last dose ± 1 wk)	Flare	Notes
		2	3	4	5	6				
Study Visit	1									
Study Weeks	0	4 ± 1 wk	8 ± 1 wk	12 ± 1 wk	16 ± 1 wk	20 ± 1 wk				
Informed consent	X									
Inclusion and exclusion criteria	X									
Demography	X									
Full physical examination including height and weight	X									
Past and current medical conditions	X									
Urine pregnancy test (WOCBP only) – serum test if locally required	X	X	X	X	X	X	X	X	Test is required for WOCBP on study treatment until the last follow-up.	
Clinical safety laboratory assessments (include liver chemistries)	1	2	2	2	2	1	1	2	1: Hematology, chemistry, aldolase, troponin, urinalysis 2: Hematology, chemistry, aldolase, troponin	
PK	X					X	X	X		
Immunogenicity (Anti-drug antibody)	X					X	X	X		

Procedure	Screening/Baseline	20-Week Treatment Period					WD (4 weeks post-last dose) ± 1 wk	Study Visit 7 Additional follow-up (12 weeks post-last dose ± 1 wk	Flare	Notes
		2	3	4	5	6				
Study Visit	1									
Study Weeks	0	4 ± 1 wk	8 ± 1 wk	12 ± 1 wk	16 ± 1 wk	20 ± 1 wk				
Sample collection for optional biomarker sub-study	X					X	X		X	Sample collection for the optional biomarker sub-study should be done after obtaining a written consent.
12-lead ECG	X					X	X			
Vital signs	X	X	X	X	X	X	X		X	
HES Core Assessments/HES flare details	X	X	X	X	X	X	X		X	
Study treatment	X	X	X	X	X					
AE review	X	X	X	X	X	X	X	X	X	
SAE review	X	X	X	X	X	X	X	X	X	
Concomitant medication review	X	X	X	X	X	X	X	X	X	

wk: week

- The baseline visit is the exit visit (32 weeks after randomization) for Study 200622. Assessments that are captured as part of the exit visit for Study 200622 do not have to be repeated. Information will be transferred accordingly.
- Biological sample collection (for clinical safety laboratory, PK, and immunogenicity) is done prior to administration of study treatment on dosing visits (Visits 1, 2, 3, 4, 5) as specified in the SoA.
- WD: Prematurely discontinuation of mepolizumab (~4 weeks after the last dose of mepolizumab).
- Visit 7 - Additional follow-up is required 12 weeks after the last dose of mepolizumab for participants who do not continue with mepolizumab via mepolizumab HES expanded access at that time.

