2.2. Study Design

Overview of Study Design and Key Features	

↑: Mepolizumab treatment (300mg SC per administration) V: Visit ^: Participants who continue with mepolizumab treatment via MHE104317/MHE112562 after Study 205203 will have the last assessment on Week 20 (Visit 6). #: Participants who do not continue with mepolizumab via MHE104317/MHE112562 after Study 205203 will have additional follow-up 12 weeks after the last dose (Visit 7).
	
Design Features	
 Multi-centre, open-label extension, 20-week treatment period, safety study of mepolizumab in adolescent and adult participants with HES who took part in the phase 3 study 200622. Visit 1 for study 205203 is the exit visit (32 weeks after randomisation) for study 200622. Investigators will be blinded to the blood eosinophil count from the sample obtained at visit 1 (first dosing visit), in order to maintain the blinding of study 200622, after which eosinophil counts will be unblinded starting from visit 2. Investigators may adjust the participants' background HES therapy per standard of care starting at visit 2 (approximately 4 weeks after the first dose of open-label mepolizumab). Participants who withdraw from study treatment prematurely should continue in the study per protocol until 20 weeks from first dose of open-label mepolizumab. Participants who complete assessments at visit 6 (week 20) may continue with mepolizumab treatment via MHE104317/MHE112562, where local regulation permits. Study participants who do not continue with MHE104317/MHE112562 will have an additional follow-up assessment 12 weeks after the last dose of mepolizumab.
Dosing	
 300 mg SC mepolizumab every 4 weeks (5 administrations) while continuing their HES therapy. The final dose of study treatment will be administered at Visit 5 (Week 16) with completion of the study treatment period achieved at the next 4-weekly visit.

Overview of Study Design and Key Features	
Time & Events	
 See Appendix 1: Schedule of Activities
Treatment Assignment	
 All participants are assigned to 300mg SC mepolizumab. Between 80 and 120 participants will be randomised in study 200622. Those participants who complete required assessments for 32 weeks starting from randomisation may be evaluated for eligibility to study 205203.

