The definition of HES flare for this study (205203) is different from that for the preceding, randomized Study 200622. This difference in definitions is due to the requirement during Study 200622 to avoid decreases in background HES therapy that may confound a blinded subject’s clinical status as well as the requirement in Study 200622 to blind blood eosinophil levels. In Study 205203, all participants will receive mepolizumab and investigators will be unblinded to blood eosinophil levels starting 4 weeks after the first dose (Visit 2) so that they may adjust background HES therapy as per SoC.

Rate of HES Flares

- For subjects completing the study, the rate of HES flares will be calculated as

$$\frac{365.25 \times \text{Number of observed HES flares}}{\text{Date of Week 20 (Visit 6)} - \text{Date of first dose of mepolizumab} + 1}$$
- For subjects withdrawing prematurely from the study, the rate of HES flares will be calculated as

$$\frac{365.25 \times \text{Number of observed HES flares}}{\text{Date of study withdrawal} - \text{Date of first dose of mepolizumab} + 1}$$

The number of HES flares is the number of unique starting dates for HES flares. To be considered as a separate episode of HES flare, the start date of an HES flare must be at least 14 days apart from the resolution date of the preceding HES flare.

Oral Prednisone Equivalent Daily Dose

- For each subject, oral prednisone equivalent daily dose (mg) on each day of the study will be identified from the concomitant medications page
- Partial start and end dates for concomitant medications will be handled as described in Section 13.5.2.
- Corticosteroids will be identified from the list of coded concomitant medications for the study, by merging with the GSK respiratory medication class (RMC) reference data set by component code. This reference data is created by dictionary specialists who identify a list of component terms for corticosteroids, which then undergo clinical review to ensure the correct classification is assigned.
- Only corticosteroids recorded with route = “PO” will be considered as oral corticosteroids.
- Subjects not receiving OCS therapy on any day of the study will be assigned a prednisone equivalent daily dose of 0 mg for that day.
- The corticosteroid conversion factors in the table below will be used to scale each corticosteroid dose to a prednisone equivalent dose.

Medication Name	Scaling Factor
Betamethasone	8.33
Budesonide ¹	0
Cortisone	0.2

Dexamethasone	6.67

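### A flare escalated at Visit 1 before the first injection enters the open-label flare rate, although it arose under Study 200622 treatment

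*Protocol*

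**What the plan says.** SAP 2.2 states that "Visit 1 for study 205203 is the exit visit (32 weeks after randomisation) for study 200622". It is also the first dosing visit. The Schedule of Activities marks HES Core Assessments and flare details at Visit 1 and adds: "Assessments that are captured as part of the exit visit for Study 200622 do not have to be repeated. Information will be transferred accordingly".

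Protocol 9.1.1 requires investigators to "record details pertaining to the HES flare event in the CRF from Visit 1 until 20 weeks after the first dose of mepolizumab". The same section fixes the onset: "The start date for an HES flare will be defined as the date of therapy escalation confirmed by the investigator".

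SAP 9.1.1.1 and 13.4.4 count unique flare start dates. They divide by the time from first dose to the Week 20 visit (or withdrawal), plus one day, so the first-dose date is inside observed time. A separate rate is computed from 200622 data in the same subjects. SAP 9.1.1.4 labels the two periods Week 0 to 32 and Week 32 to 52. To count as a separate episode, "the start date of an HES flare must be at least 14 days apart from the resolution date of the preceding HES flare".

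**The concern.** One clinic day closes the double-blind study and opens the extension. The investigator assesses the participant at every clinic visit and decides whether worsening supports more therapy (Protocol 9.1.2), so escalations dated on visit days are to be expected. By Visit 1 the last 200622 dose was given about four weeks earlier (Protocol 12.2). Worsening found that day before the injection reflects double-blind treatment, yet the counting rules make it an open-label event.

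Table 3.3 sets the 200622 rate beside the 205203 rate, and SAP 5.1 presents results by previous treatment. In the previous-placebo group the misassigned flares come from the placebo period. They raise the open-label rate and blur the comparison the table displays.

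**Working it through.** The plan states no expected flare rate or sample size for this endpoint, so there is no planned figure to reproduce. The check traces the rules and then sizes the effect.

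**Tracing a pre-dose flare escalated at Visit 1**

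1. It is recorded, because recording opens at Visit 1 rather than at first dose (Protocol 9.1.1).
2. Its start date is the first-dose date, which is Study Day 1 (SAP 13.4.1).
3. It is in the numerator, because no sentence excludes pre-dose flares (SAP 9.1.1.1, 13.4.4).
4. Its day is in the denominator (SAP 13.2, 13.4.4).
5. The requirement that therapy be unchanged for at least 4 weeks does not generally remove it. Study 200622 holds background therapy constant unless symptoms worsen (Protocol 5.4), so the condition will usually be met at Visit 1.

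Two SAP conventions show the gap. SAP 5.2 assumes that Visit 1 assessments precede the first dose when no time is collected. SAP 13.2.1 gives adverse events a pre-treatment category by date or date and time. Flares have no such category. SAP 13.5.2 moves some partial flare dates to the first-dose date and treats those flares as starting on treatment.

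The Week 20 visit date is also inside the window, so flares arising in the last open-label interval and treated at Visit 6 are already counted. Visit 1 flares are a net addition, with no offsetting loss at the other end.

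**Size per flare**

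A nominal completer has 140 + 1 = 141 days.

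- Individual rate: 365.25 / 141 = 2.59/year. Over the ±1 week Week 20 window, 365.25/148 = 2.47 to 365.25/134 = 2.73.
- Crude group effect of one flare: 1 / (n × 141/365.25). The number enrolled is not given. Study 200622 randomises 80 to 120; 60 is an assumed lower value.

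| n | Person-years | Per flare (/year) | Five flares (/year) |
|---|---|---|---|
| 60 | 23.16 | 0.043 | 0.216 |
| 80 | 30.88 | 0.032 | 0.162 |
| 120 | 46.32 | 0.022 | 0.108 |

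**Relative inflation (illustration)**

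Assumptions: 30% of subjects flare in 32 weeks (224 days); a share f of the flares from the last 4-week interval of 200622 is treated at the exit visit; r is the open-label rate divided by the rate in that interval. The documents give neither f nor r. The 30% is borrowed from the monitoring threshold in Protocol 5.2 and is not a forecast.

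- Implied rate: −ln(0.7) / (224/365.25) = 0.58/year.
- At n=80 and r=1: expected flares in the last 4 weeks, 0.5816 × 80 × 28/365.25 = 3.57; in the open-label period, 0.5816 × 30.88 = 17.96.
- f = 0.10: 0.36 extra flares, 0.36/17.96 = +2%, so the rate goes from 0.58 to 0.59.
- f = 0.50: 1.78 extra flares, 1.78/17.96 = +10%, so the rate goes from 0.58 to 0.64.
- In general the inflation is about f/(5r), since 20 weeks hold five 4-week intervals. At r = 0.5, as might apply in the previous-placebo group, f = 0.10 to 0.50 gives +4% to +20%.

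**The case against.** **The SAP already has a rule.** SAP 13.2 classifies events by time relative to the first open-label dose. The flare CRF is not among the documents, dose time is recorded (Protocol 7.5), and each flare has a narrative (Protocol 9.1.2). The information to separate pre-dose from post-dose flares may therefore exist. That stands, but no flare derivation tells anyone to use it, and the written start is a date.

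**Double counting.** A reader might infer that the same flare is certainly counted in both studies, because both period labels name Week 32. The documents do not support that. The 200622 protocol and its flare cut-off are not supplied, and its definition differs (Protocol 9.1.1). SAP 5.2 lists laboratory, PK, immunogenicity and vital-sign data as carried over and does not name flare details. A flare counts twice only if it was recorded in both studies and meets both definitions. Nothing prevents this, and nothing shows it.

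**Size.** A reader might also infer an inflation of 20% to 40%. At r = 1, 20% needs every escalation to fall on a scheduled visit day; 40% needs that and a halved rate. The plan provides for unscheduled flare visits, telephone evaluation and escalation by non-study physicians, so that is an extreme bound.

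**Look-back.** The 4-week stability condition already blocks a new Visit 1 flare when therapy was escalated within the previous four weeks. Only longer unresolved 200622 flares are left open by the separation rule.

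**Importance.** The endpoint is exploratory, there is no hypothesis test (SAP 2.3), and the two rates already rest on different flare definitions. This limits the weight of the point. It does not justify attributing a pre-dose flare to the open-label drug.

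**Conclusion.** The concern holds as a misattribution that follows from applying the written rules. A flare escalated at Visit 1 before the first injection enters the 205203 rate. Double counting is possible but not established.

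The size per flare is firm given nominal visit timing. The relative inflation of about 2% to 10% rests on the assumed share treated at the exit visit and on a constant rate; it would be larger in the previous-placebo group if flares become less frequent on mepolizumab. The error affects a descriptive exploratory rate and no test. It is worth correcting because flare rate is the one efficacy endpoint that is modelled, and the correction is cheap.

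**What to change.** In SAP 9.1.1.1 and 13.4.4:

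- Exclude from the 205203 count any flare whose escalation date is on or before the first-dose date, unless the recorded time or the flare narrative shows that it arose after the dose. This also covers a flare recorded between Visit 1 and a later first dose.
- Count an excluded flare in the 200622 rate only if it meets the 200622 definition. List any flare that falls in neither rate.
- Keep in the 205203 count any flare whose partial date is imputed to the first-dose date under SAP 13.5.2, so that the worst-case convention is preserved.
- State that the 14-day separation rule looks back to the resolution date of the last 200622 flare.

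The extra day in observed time can stay. It is 1/141, about 0.7%, of a completer's time, and removing it would conflict with the observed-time and study-day definitions in SAP 13.2 and 13.4.1.

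The cost is SAP wording, a date condition with one exception, and review of the few flares dated on the first-dose date. The 200622 flare data are already needed for Table 3.3. A few flares leave the 205203 count, possibly including a rare true same-day post-dose escalation whose timing was not documented.
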